9.4.3 ANALYSIS OF THE SECONDARY ENDPOINT(S)

H2: Providers in the CDS and CDS-E strategy arms will increase their likelihood of satisfying the composite endpoint defined by: 1) prescribing or recommending non-opioid analgesics at the extraction encounter and 2) not prescribing opioids at the index encounter for patients following extractions more than providers in the SP arm.

Analysis plan: Hypothesis H2 posits that patient encounters at which extractions are performed by dental providers in the CDS and CDS-E arms will have a larger increase in the likelihood of receiving a prescription or recommendation for non-opioid analgesics and not prescribing opioids at the index encounter than patient encounters in the SP arm when comparing independent samples of patient encounters before the implementation to patient encounters following the implementation. The same analytic strategy used for the primary endpoint will be used for this secondary endpoint and will be conducted on the Intention to Treat Analysis Dataset.

H3 (alternative): Patients will report higher levels of the extent of shared decision making in the CDS-E arm than the CDS or SP arms.

Analysis plan: Hypothesis H3 posits that patients will report higher levels of the extent of shared decision making in the CDS-e arm than CDS or SP arms during the strategies implementation time period. A general linear mixed-model regression with an identity link and normal error distribution will be used to test the effects of the implementation strategies. The patient-level endpoint is the score on the 3-item composite of adapted Collaborate Shared Decision Making, and is considered an interval-level variable. This endpoint will be predicted by 2 fixed-effects terms for study arm of CDS (CDS vs. SP) and CDS-E (CDS-E vs. SP). A random intercept for provider will be included in the model. Additional covariates to be included will be described in the MOP. Model-predicted means and confidence intervals for the endpoint will be summarized by study arm. A contrast will estimate the difference in the mean of the endpoint for patients in the CDS-e arm vs. CDS and SP (pooled). This analysis will be conducted on the Intention to Treat Analysis Dataset.

H4 (descriptive): Compare patient report of mean pain in the week following tooth extraction across the 3 study arms.

Analysis plan: This analysis is descriptive, and will comparison across study arms the mean pain rating in the 3-6 days since the extraction encounter, self-reported by patients within 6 days of the extraction encounter. A general linear mixed-model regression with an identity link and normal error distribution will be used to estimate the mean and 95% CI of the pain rating for each study arm. The model will include 2 fixed-effects terms for study arm of CDS (CDS vs. SP) and CDS-E (CDS-E vs. SP). A random intercept for provider will be included in the model. Additional covariates to be included will be described in the MOP. Model-predicted means and confidence intervals for the endpoint will be summarized by study arm. This analysis will be conducted on the subset of the Intention to Treat Analysis Dataset who complete a patient survey.

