1 PROTOCOL SUMMARY

1.1 SYNOPSIS

Title:

De-Implementing Opioid Use and Implementing Optimal Pain Management Following Dental Extractions

Study Description:

The overarching goal of this project is to de-implement the reliance on opioid analgesics and to implement reliance on non-opioid analgesics to manage pain following dental extractions. Using a prospective, 3-arm cluster randomized trial design with dentists as the unit randomized and patient-level prescribing data as the primary outcome, the study team will compare different strategies to reduce the reliance on opioids and increase the use of alternative pain management approaches utilizing information support tools aimed at both providers and their patients.

Objectives:**Primary Objective:**

(1) To test the efficacy of two interventions (Clinical Decision Support with and without Patient Education), compared to treatment-as-usual to decrease opioid prescribing for dental extractions.

Secondary Objectives:

(1) To test the efficacy of two interventions (Clinical Decision Support with and without Patient Education), compared to treatment-as-usual to increase exclusive non-opioid pain management for dental extractions.

(2) To compare the degree to which each of the 3 study arms (Clinical Decision Support with and without Patient Education, and treatment-as-usual), facilitates shared provider and patient decision-making concerning pain management options for dental extractions.

(3) To explore whether the study interventions lead to differences in patient experiences of post-extraction pain.

Endpoints:**Primary Endpoint:**

(1) Differential pre- to post-intervention change by study arm in the percentage of extraction encounters with an opioid prescribed.

Secondary Endpoints:

(1) Differential pre- to post-intervention change by study arm in the percentage of extraction encounters at which a provider recommended NSAIDs and/or APAP and did not prescribe opioids at the extraction encounter.

(2) Study arm comparison of the mean of the patient-reported shared decision making composite score (composite of 3 components concerning management of post-extraction pain options: effort to explain, to listen, and to personalize)

(3) Study arm comparison of the average patient-reported pain in 3-6 days following the extraction.

[figure not shown]
Study Population:

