3 OBJECTIVES AND ENDPOINTS

OBJECTIVES	ENDPOINTS	JUSTIFICATION FOR ENDPOINTS
Primary		
To test the efficacy of two interventions (Clinical Decision Support with and without Patient Education), compared to treatment-as-usual to decrease opioid prescribing for dental extractions.	Differential pre- to post-intervention change by study arm in the percentage of extraction encounters with an opioid prescribed (during the day of the extraction encounter).	A prescription is legally required for opioids to be dispensed. Prescriptions are reliably and routinely entered in the electronic health record.
Secondary		
To test the efficacy of two interventions (Clinical Decision Support with and without Patient Education), compared to treatment-as-usual to increase exclusive non-opioid pain management for dental extractions.	Differential pre- to post-intervention change by study arm in the percentage of extraction encounters at which a provider prescribed or recommended non-opioid analgesics (ibuprofen, naproxen, aspirin, or acetaminophen) and did not prescribe opioids (at the time of the extraction encounter).	A discrete data element in the electronic health record exists for documenting a non-opioid recommendation. Documentation standards ensure these are routinely documented.
To compare the degree to which each of the 3 study arms (Clinical Decision Support with and without Patient Education, and treatment-as-usual), facilitates shared provider and patient decision-making concerning pain management options for dental extractions.	Study arm comparison of the mean of the patient-reported shared decision-making composite score (composite of 3 components concerning management of post-extraction pain options: effort to explain, to listen, and to personalize 3-6 days after the extraction encounter)	Patient report best captures the patient experience of the encounter. This is a modification validated, succinct patient-reported outcome measure used to demonstrate the extent of shared decision making.
To explore whether the study interventions lead to differences in patient experiences of post-extraction pain.	Study arm comparison of the average patient-reported pain following the extraction (3-6 days after the extraction encounter).	Patient report best captures pain experience. The Numeric Rating Scale is a validated patient-reported outcome measure used to measure pain level in research and clinical practice.

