6 STUDY INTERVENTION

6.1 STUDY INTERVENTION(S) ADMINISTRATION

6.1.1 STUDY INTERVENTION DESCRIPTION

The study intervention will be active within HealthPartners Dental Group for 12 months or until patient accrual goals are met. After completion of the study, the HealthPartners Dental Group will decide whether to continue its activity, but this will be beyond the study's scope.

Standard Practice: Providers will not receive point of care decision support, serving as the control group representing usual care. Patients will receive usual dental care.

CDS: Providers will receive point of care decision support to guide pain management recommendations and prescribing for patients who receive dental extractions. The clinical decision support will highlight: (1) potential medication interactions between the patient's current medications and commonly recommended analgesics for patients following dental extractions; (2) relevant health conditions that may impact pain management strategies; and (3) automated access to the Prescription Drug Monitoring Program. Patients will receive usual dental care [when implemented by HealthPartners Dental Group: access to the Prescription Drug Monitoring Program via the clinical decision support tool will be suspended to align with the organization approach via the electronic health record].

CDS-E: Providers will receive point of care decision support to guide pain management recommendations and prescribing related to dental extractions. The clinical decision support will highlight: (1) potential medication interactions between the patient's current medications and commonly recommended analgesics for patients following dental extractions; (2) relevant health conditions that may impact pain management strategies; and (3) automated access to the Prescription Drug Monitoring Program [when implemented by HealthPartners Dental Group: access to the Prescription Drug Monitoring Program via the clinical decision support tool will be suspended to align with the organization approach via the electronic health record].

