In addition, patients will receive an educational handout prior to the extraction procedure comparing effectiveness for managing pain, risks and benefits of non-opioid pain medications and opioid medications. This handout intends to initiate a conversation between the patient and provider about patient needs, goals and preferences. The patient will also receive an education handout about pain management after dental extraction for their reference. This handout intends to normalize the experience of some discomfort and to help patients decide about whether to contact their provider for additional help to manage their pain after extraction. Patients will receive usual dental care.

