9 STATISTICAL CONSIDERATIONS

9.1 STATISTICAL HYPOTHESES

- Primary Efficacy Endpoint(s):

H1 (alternative): Providers in the CDS and CDS-E strategy arms will reduce their likelihood of prescribing opioids for patients following extractions more than providers in the SP arm.

H1 endpoint: Comparison across study arms of the differential change in percentage of permanent tooth extraction encounters having an associated opioid prescription on the day of the extraction encounter, from the one year prior to the intervention implementation to one year after the intervention implementation.

- Secondary Efficacy Endpoint(s):

H2 (alternative): Providers in the CDS and CDS-E strategy arms will increase their likelihood of prescribing or recommending non-opioid analgesics at the extraction encounter and not prescribing opioids for patients following extractions more than providers in the SP arm.

H2 endpoint: Comparison across study arms of the differential change in percentage of permanent tooth extraction encounters having both 1) a prescription or recommendation in the treatment plan for non-opioid analgesics and 2) to not have an associated opioid prescription on the day of the extraction encounter, from the one year prior to the intervention implementation to one year after the intervention implementation.

H3 (alternative): Patients will report higher levels of the extent of shared decision making in the CDS-E arm than the CDS or SP arms.

H3 endpoint: Comparison across study arms of the mean of the 3-item composite of adapted Collaborate Shared Decision Making score reported by the patient.

H4 (descriptive): Compare patient report of average pain in the week following extraction across the 3 study arms.

H4 endpoint: Comparison across study arms of the mean pain rating in the 3-6 days since the extraction encounter, self-reported by patients.

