9.4 STATISTICAL ANALYSES

9.4.1 GENERAL APPROACH

Baseline characteristics of study participants will be summarized with mean and standard deviation for interval data and proportions for categorical data. General and generalized linear mixed models will be used to test study arm differences in endpoints. Models will include terms for study arm, time (for models assessing change from pre- to post-intervention), and their interaction. Covariates to be included in models will be described in the Manual of Procedures (MOP). A random intercept for provider will be included in models to account for the cluster-randomized design with providers as the unit randomized. Differential change will be compared for each study arm via a series of planned contrasts. Study arm contrasts will be tested at alpha=0.05 and all tests will be two-sided. Model-predicted means and proportions along with 95% confidence intervals will be used to assess the magnitude, direction, and precision of intervention effects.

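### H3 claims more shared decision making with CDS-E than with CDS or SP, but its only named contrast pools CDS with SP, and no interval or test for CDS-E minus CDS is planned

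*Combined protocol and SAP*

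**What the plan says.** Sections 9.1, 9.2 and 9.4.3 all state H3 in the same terms: "Patients will report higher levels of the extent of shared decision making in the CDS-E arm than the CDS or SP arms". The matching objective in section 3 begins "To compare the degree to which each of the 3 study arms", and the synopsis endpoint is "Study arm comparison of the mean of the patient-reported shared decision making composite score", with no pairs named.

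Section 9.4.3 fits a linear mixed model with a random provider intercept and two arm terms, CDS against SP and CDS-E against SP. It plans two outputs. The first is arm-level: "Model-predicted means and confidence intervals for the endpoint will be summarized by study arm". The second is one contrast: "A contrast will estimate the difference in the mean of the endpoint for patients in the CDS-e arm vs. CDS and SP (pooled".

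Section 9.4.1 adds a general rule, "Study arm contrasts will be tested at alpha=0.05 and all tests will be two-sided", again without saying which arms are contrasted. The text defers stratification factors to a Statistical Analysis Plan (section 6.3) and covariates to the Manual of Procedures (sections 9.4.1 to 9.4.3). It does not defer contrasts.

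**The concern.** The hypothesis names two comparators and the test has one, a blend of the two. On the natural reading, H3 is a claim about each comparator, and CDS-E against CDS is the comparison that isolates patient education, since both arms have the decision support and only CDS-E adds the handouts. The pooled contrast cannot deliver that claim, because a benefit over SP alone is enough to make it positive.

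If decision support alone improved the conversation and the handouts added nothing, a significant pooled result could still be reported as support for H3, and so for education over CDS. The planned arm means would show the direction of CDS-E minus CDS. Without an interval for that difference, they would not show whether it can be told apart from zero.

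**Working it through.** **The algebra.** With equal weights, pooled contrast = CDS-E − (CDS + SP)/2 = ½(CDS-E − CDS) + ½(CDS-E − SP).

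- If CDS-E = CDS = SP + d, the contrast is d/2, not zero.
- If CDS-E is 0.4 SD above SP and CDS is 0.5 SD above SP, the contrast is 0.4 − 0.25 = +0.15 SD, although CDS-E is worse than CDS.

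This needs no assumption about ICC or effect size.

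**Inputs from the documents.**
- Surveys: 1,520 approached at a 79% response rate (section 9.2). 1,520 × 0.79 = 1,200.8, which reproduces the stated 1,200.
- Providers: target 51, allocated 1:1:1 (section 4.1), so 17 per arm.
- Section 6.3 aims for similar survey counts by provider and arm. I take 1,200/3 = 400 surveys per arm and m = 400/17 = 23.53 per provider.
- Two-sided alpha 0.05 (section 9.4.1).

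**Assumptions.** The documents give no SD, effect size or ICC for this score. The ICC is therefore varied from 0 to 0.30; 0.3 is the only ICC in the documents and belongs to opioid prescribing. Effects are in SD units. Degrees of freedom are 51 − 3 = 48, critical value 2.011.

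**Formulas.**
- Design effect DE = 1 + 22.53 × ICC.
- SE of the pooled contrast = √(DE × (1/400 + 1/800)).
- SE of CDS-E minus CDS = √(DE × 2/400). The ratio of the two is √(4/3) = 1.155.
- Chance that the pooled contrast is significant: noncentral t, 48 df, true value d/2.
- Shares among significant trials: simulated arm means with a shared 48-df variance estimate.

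**Results when CDS = CDS-E = SP + 0.3 SD** (true pooled contrast 0.15 SD, true CDS-E minus CDS zero).

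| ICC | 0 | 0.02 | 0.05 | 0.10 | 0.30 |
|---|---|---|---|---|---|
| DE | 1.00 | 1.45 | 2.13 | 3.25 | 7.76 |
| SE pooled (SD) | 0.061 | 0.074 | 0.089 | 0.110 | 0.171 |
| SE CDS-E minus CDS (SD) | 0.071 | 0.085 | 0.103 | 0.128 | 0.197 |
| Pooled contrast significant for CDS-E | 67% | 51% | 38% | 27% | 14% |
| Of those, CDS-E mean observed above CDS mean | 71% | 81% | 90% | 95% | 99% |
| Of those, 95% CI for CDS-E minus CDS includes zero | 96% | 95% | 93% | 91% | 82% |

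For d from 0.2 to 0.4 SD and all these ICCs, the chance of a significant pooled contrast runs from 8% to 89%; at ICC 0.30 it runs from 8% to 21%. The second case above, with CDS-E 0.1 SD worse than CDS, has the same contrast value of 0.15 SD and so the same rates as the fourth row.

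These are not type I error rates, since the pooled contrast is truly non-zero. They show how often a correct rejection would be open to the wrong reading.

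**The case against.** The best defense is that H3 can be read as comparing CDS-E with the two arms that lack patient education, taken together. The design supports this. Of the pre-extraction handout, given only in CDS-E, section 6.1.1 says "This handout intends to initiate a conversation between the patient and provider about patient needs, goals and preferences"; of patients in the CDS arm it says "Patients will receive usual dental care". On that reading the contrast is right and only the wording of H3 is loose. This stands as a possible reading, and it is why the pooled test should be kept. It does not remove the mismatch: the objective speaks of each of the three arms, and the hypothesis as worded permits a claim over CDS that the test does not support.

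A second defense is that the planned arm means with intervals already protect the reader. In an unadjusted analysis with independent arms, whenever the interval for CDS-E minus CDS includes zero, the two arm intervals overlap. That is true, but overlap does not settle the question. With equal arm standard errors s, the difference interval excludes zero beyond 2.011 × √2 × s = 2.84s, while the arm intervals overlap up to 2 × 2.011 × s = 4.02s. Between those values overlap would mislead in the other direction. A reader could approximate the difference interval from the two arm intervals, but covariate adjustment makes that inexact.

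Third, the size is not anchored in the documents, and at high ICC the misleading result is uncommon. That is fair, and the percentages are illustrations only. The algebra does not depend on them.

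Finally, contrasts might be specified in a document not supplied. Nothing in the text says so.

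**Conclusion.** The concern holds. The hypothesis and its only named contrast make different claims, and no interval or test is planned for CDS-E minus CDS. A significant pooled result supports CDS-E over the average of the other two arms and nothing more specific.

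How often this would mislead depends on the assumed effect and ICC, on equal surveys per arm and provider, and on CDS truly matching CDS-E. No document quantifies that last scenario. The consequence is limited to what can be concluded from one secondary endpoint; H1 is untouched. It should still be corrected, because the correction is cheap and changes what a significant H3 result may be said to show.

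**What to change.** In section 9.4.3, keep the pooled contrast as the H3 test. Add CDS-E minus CDS and CDS-E minus SP, each with a 95% CI from the same model. Label both as estimation only, because the general rule in section 9.4.1 would otherwise turn them into further tests at 0.05. CDS-E minus SP is already a model term, so only CDS-E minus CDS is new.

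Reword H3 in sections 9.1, 9.2 and 9.4.3 to say that shared decision making is *higher in CDS-E than in the CDS and SP arms combined*. State that a significant pooled result does not establish CDS-E above CDS.

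**Cost.** Two contrasts from a model already fitted, a few sentences, and no new data. The power of the pooled test is unchanged, but its claim is narrower. The CDS-E minus CDS interval would have a half-width (2.011 × SE) of about 0.14 / 0.17 / 0.21 / 0.26 / 0.40 SD at ICC 0 / 0.02 / 0.05 / 0.10 / 0.30, so it is imprecise if the ICC is high.

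**Option.** Only if the sponsor wants to claim superiority over each arm, require both pairwise contrasts to be significant in favor of CDS-E. This is a real trade-off. With CDS = SP and CDS-E 0.3 SD higher, power falls from 98% to 88% at ICC 0.02, from 91% to 71% at 0.05, from 76% to 48% at 0.10 and from 41% to 18% at 0.30.

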9.4.4 SAFETY ANALYSES

The study does not include objectives or formal endpoints concerning safety. However, potential harm monitoring activities will be conducted as described in section 8.2, and analysis activities conducted as described below.

Identify whether the CDS inappropriately fires or inappropriately offers considerations

The frequency of notifications and content areas (usability, potential safety, or other) will be summarized by study arm (CDE or CDS-E) and provider type.

Identify potential adverse events

Frequencies, proportions and 95% confidence intervals on proportions of patients having hospitalizations documented in the HealthPartners electronic health record within 72-hours of the extraction encounter deemed as adverse events will be summarized by study arm. The

patient encounter study population for H1 and H2 for patients seen following the implementation of the interventions will be used for this analysis. Events with non-overlapping confidence intervals on the proportions by study arm will prompt the study team to assess diagnostic codes related to the encounters from the electronic health record. Frequencies and proportions of diagnostic codes by study arm will be computed.

